4.3. Claims and Intended Performance

The proposed intended use statement for DreamKit is as follows, with the parts relevant to this study bolded (wording may change before regulatory submission):

The DreamKit device is a physiologic data recorder intended to collect and record data for use by clinical software used in polysomnography and sleep disorder studies for the diagnosis of sleep related breathing disorders. The Plethysmography-Acquired Respiratory Effort (PARE) algorithm provides a respiratory effort signal acquired from the DreamKit photoplethysmography signal that correlates with traditional respiratory effort signals used in polysomnography. The DreamKit with PARE provides the information required to detect apneas and hypopneas and classify these respiratory events as central, mixed, or obstructive. It is intended for adult use and can be used in a hospital, clinic, or patient home.

5. STUDY DESIGN

5.1. Overall Design

This is an interventional study performed in a single center for validation purposes, with all data collection occurring within a single visit.

Up to 20 participants will be enrolled, in order for up to ten to complete data collection. Completion of the protocol by an individual participant will require an office visit of approximately one hour followed by a laboratory visit of approximately three hours during the day, to take place within a four week period. If convenient, the two visits may be combined. Total enrollment duration for an individual participant will not exceed four weeks; it is estimated that the entire study duration will not exceed six months.

5.2. Scientific Rationale for Study Design

5.2.1. Data collection from healthy participants during wakefulness

The purpose of this study is to compare two continuous signals and demonstrate that the DreamKit respiratory effort signal aligns with the esophageal pressure signal. We chose to collect data during wakefulness in order to coach participants through various breathing maneuvers that mimic a range of

Document ID:	SRC_SLE_Sparkle EP 2_2021_11315	Document title:		Classification:	Confidential
Modified:	12 May 2021	Clinical Investigation Proto	Clinical Investigation Protocol ICH E6 Aligned		
Version:	1	User Tool ID:	16.2.6UserTool0004		
Status:	FINAL	User Tool Version Date	5June2019	Page:	14

respiratory patterns characteristic of sleep-disordered breathing, as described in Section 9.1.3. The breathing maneuvers were designed to manipulate the rate, amplitude, and phase of the signals as much as possible, in contrast to collecting the data during sleep, which would have led to recordings with mostly relaxed breathing interrupted by respiratory events that may not represent the full range of apneas, hypopneas, and RERAs. In addition, overnight esophageal manometry is now performed very rarely as it is not well-tolerated during sleep. The decision to collect data during wakefulness means that there is no need to target those with diagnosed sleep-disordered breathing, whose breathing during wakefulness is not disordered.

The study design we have adopted here is analogous to the requirements for validating a pulse oximetry signal per ISO 80601-2-61, in which ten healthy participants are required to breath a gas mix that results in oxygen saturation ranging from 70-100%, in order to validate the pulse oximeter against oxygen saturation determined by the gold-standard of arterial blood samples.

5.2.2. Identification of the comparator

Esophageal manometry is now rarely included in PSGs; instead, the 'clinical standard' for assessing respiratory effort is belts worn around the thorax and abdomen. It is important, however, that any estimate of respiratory effort is compared against the gold-standard, which in this case is esophageal pressure. Referring to the pulse oximeter example described above, comparison to esophageal pressure rather than thoracic/abdominal belts is akin to comparison to arterial blood samples rather than a previously-validated pulse oximeter.

5.2.3. Adoption of respiratory effort amplitude as the primary endpoint

The three characteristics of a continuous signal are amplitude (in this case, respiratory effort in pressure units of cmH₂O), frequency (in this case, breathing rate), and phase (in this case, time alignment of the two signals). The most clinically-relevant of these characteristics is amplitude, as the only component of the respiratory effort signal taken into account when scoring PSGs and HSATs is whether or not respiratory effort is present or absent during apneic events or whether there is reduction in respiratory effort that is proportional to the flow reduction during hypopneic events (AASM scoring criteria; Version 2.6). We will undertake exploratory analyses of respiratory rate (breaths/minute) and phase (time alignment).

5.2.4. Analysis of the primary endpoint breathing conditions

Attempting to breathe against an occluded airway is an essential characteristic of an obstructive apnea, while cessation of breathing following expiration is characteristic of a central apnea. Attempting to breathe against a resistor limiting the flow during inspiration or expiration characterizes respiration during an obstructive hypopnea or respiratory-effort related arousal (RERA), while unresisted shallow breathing is characteristic of a central hypopnea. Our primary analysis will therefore be based on breathing conditions representative of every respiratory event that relies on the respiratory effort signal per the AASM scoring

Document ID:	SRC_SLE_Sparkle EP 2_2021_11315	Document title:		Classification:	Confidential
Modified:	12 May 2021	Clinical Investigation Protocol ICH E6 Aligned			
Version:	1	User Tool ID:	16.2.6UserTool0004		
Status:	FINAL	User Tool Version Date	5June2019	Page:	15

manual (Version 2.6). Additional manipulations of the signal (relaxed, fast, and slow breathing) will be used for exploratory analyses.

5.2.5. Identification of performance target

We adopted a performance target of 0.5 for the ICC of respiratory effort amplitude between the DreamKit and esophageal manometry signals in order to demonstrate 95% confidence of at least moderate agreement between signals.⁶

5.3. End of Study Definition

The study will be considered complete when participants are no longer being examined or the last participant's last study visit has occurred.

A participant is considered to have completed the study if he or she has completed all phases of the study including the last visit or the last scheduled procedure shown in the Schedule of Activities.

6. STUDY POPULATION

6.1. Inclusion Criteria

Subjects must meet all of the following inclusion criteria:

- Aged ≥18 years;
- · Fluent in English;
- · Able to provide informed consent.

6.2. Exclusion Criteria

Subjects shall be excluded if any of the following are present:

- Contraindication to esophageal pressure monitoring, including a sensitive gag reflex (determined by a positive response to the screening question "do you sometimes or often gag while brushing your teeth?"), dysphagia, nasal obstruction, and/or esophageal disorder likely to impact placement of the balloon:
- Pregnancy or planned pregnancy during the study (self-reported);
- History of allergic reactions to medical adhesives;
- Known allergy to lidocaine;
- Known seizure disorder;

Document ID:	SRC_SLE_Sparkle EP 2_2021_11315	Document title:		Classification:	Confidential
Modified:	12 May 2021	Clinical Investigation Protocol ICH E6 Aligned			
Version:	1	User Tool ID:	16.2.6UserTool0004		
Status:	FINAL	User Tool Version Date	5June2019	Page:	16

- Severe medical condition (controlled or uncontrolled) impacting breathing including neuromuscular disease, chronic obstructive pulmonary disease, respiratory failure or insufficiency, or requirement for oxygen therapy;
- Chronic cardiopulmonary or renal disease, including a history of irregular heart rhythms or dyspnea;
- At risk for excessive bleeding including use of anticoagulants;
- An employee, or spouse of an employee, of a company that designs, sells, or manufactures sleep related products (including Philips);
- An employee, or spouse of an employee, of PCCAB.

6.3. Enrollment

Participants who sign the informed consent form will be screened for eligibility at Visit 1. Participants meeting all enrollment criteria will be enrolled into the study.

6.4. Screen Failures

Participants who are consented to participate in the study, but who do not meet one or more criteria required for participation, are considered screen failures. Minimal information will be collected for such participants, including demographics, screen failure details, eligibility criteria, and any AEs.

Re-screening is possible if, in the opinion of the PI or their designee, the reason for the original screen fail is likely to have changed and will not impact participant safety or data integrity. Re-screened participants should be assigned the same participant number as for the initial screening.

6.5. Strategies for Recruitment and Retention

The participants will be of both sexes, with a wide body mass index (BMI) range, in order to support generalizability of results. Due to the small sample size, no firm parameters for these measures have been determined a priori.

It is anticipated that racial/ethnic minorities will represent at least 30% of the sample.

All participants will be enrolled within the US. Recruitment will be the responsibility of the site, and will take place through a local university newspaper and online advertisements. As this study involves only two visits, it is not likely that participants will drop-out or be lost to follow-up before study completion. No specific strategies for retention are required.

7. STUDY INTERVENTION

The DreamKit device is a non-released, investigational product. The previous generation device, SomnaPatch, is released (K183625); however, the device has been modified from this version.

Document ID:	SRC_SLE_Sparkle EP 2_2021_11315	Document title:		Classification:	Confidential
Modified:	12 May 2021	Clinical Investigation Protocol ICH E6 Aligned			
Version:	1	User Tool ID:	16.2.6UserTool0004		
Status:	FINAL	User Tool Version Date	5June2019	Page:	17

The device consists of a forehead patch containing the oximeter and accelerometer, and a nasal patch for connection to the cannula. The nasal pressure signal is not required for calculation of respiratory effort, and the presence of the nasal cannula during testing will interfere with the equipment required for esophageal manometry. We will therefore use a version of the device that does not include the nasal cannula. Although this prototype device will differ from the final released version, there is no difference in function with regards to the respiratory effort signal.

Additional Philips devices include the Threshold IMT breathing trainer, the Threshold PEP positive expiratory pressure device, and the Alice 6 with Sleepware (which is already in use at the site). All are released products and will be used according to their labeling.

7.1. Acquisition and Accountability

The DreamKit devices will be shipped to the investigator. All devices (used and un-used) will be returned to the Sponsor at the end of the study. An inventory of devices will be maintained.

7.2. Formulation, Appearance, Packaging, and Labeling

The Device Label, User Manual and Operating Manual are included with the IRB submission. Some content of these documents may change before regulatory submission.

7.3. Product Storage and Stability

The DreamKit device should not be used in temperatures above 35 degrees Celsius (95 degrees Fahrenheit).

7.4. Preparation

The DreamKit devices do not require configuration prior to use. The investigator is required to peel off the adhesive backing, and place the forehead patch above the eyebrows in the center of the forehead, after thoroughly prepping the skin.

8. DISCONTINUATION/WITHDRAWAL

8.1. Discontinuation/Withdrawal from the Study

An investigator may discontinue or withdraw a participant from the study for the following reasons:

- Pregnancy;
- Significant study non-compliance;
- If any AE, laboratory abnormality, or other medical condition or situation occurs such that continued participation in the study would not be in the best interest of the participant;

Document ID:	SRC_SLE_Sparkle EP 2_2021_11315	Document title:		Classification:	Confidential
Modified:	12 May 2021	Clinical Investigation Proto	Clinical Investigation Protocol ICH E6 Aligned		
Version:	1	User Tool ID:	16.2.6UserTool0004		
Status:	FINAL	User Tool Version Date	5June2019	Page:	18

- Any disease progression or medical condition which requires discontinuation;
- If the participant meets an exclusion criterion (either newly developed or not previously recognized) that precludes further study participation.
- · At the discretion of the PI for any reason.

If a participant wishes to voluntarily discontinue from the study, they should contact the site directly. AE monitoring will continue for all participants who voluntarily discontinue the study or are withdrawn from the study by investigators.

Discontinuations, withdrawals, and participants lost to follow up will be replaced. Recruitment will continue until the evaluable dataset is complete.

8.2. Lost to Follow-Up

A participant will be considered lost to follow-up if he or she fails to return for Visit 2 and is unable to be contacted by the study site staff.

9. STUDY PROCEDURES & EVALUATIONS

9.1. Efficacy Assessments

9.1.1. Phone screening

Recruitment will be the responsibility of the site. Potential participants will be screened over the phone for eligibility, and then scheduled for an enrollment visit.

Phone screening will include questions regarding sex, height and weight (for calculation of BMI), to facilitate the recruitment of participants of both sexes with a wide BMI range.

9.1.2. Visit 1: Office visit for enrollment

Preliminary assessment of eligibility will be performed by the PI or their designee during Visit 1, which is anticipated to take approximately one hour. The PI or their designee will then describe the purpose of the study, all study procedures, and possible risks of participation. After an opportunity to ask questions, consent will be sought by the PI or their designee.

Following consent, an investigator will perform a brief medical history and physical examination, including anthropometric measurements (height; weight; neck, waist, and hip circumferences). The examination will include vital signs (blood pressure obtained while seated according to American Heart Association guidelines,⁷ pulse rate, respiratory rate,⁸ and SpO2).

Participants will complete the Fitzpatrick skin type questionnaire.9

Document ID:	SRC_SLE_Sparkle EP 2_2021_11315	Document title:		Classification:	Confidential
Modified:	12 May 2021	Clinical Investigation Protocol ICH E6 Aligned			
Version:	1	User Tool ID:	16.2.6UserTool0004		
Status:	FINAL	User Tool Version Date	5June2019	Page:	19

Skin pigmentation will be assessed with a Mexameter probe (C&K Electronic; Köln, Germany) a small hand-held tool held over the skin of the inner arm (an area with minimal sun exposure) for a few seconds that emits three light wavelengths to calculate melanin and hemoglobin content in arbitrary units on a scale of 0-999 (within ±5%).

If the participant is found to be eligible, they will be scheduled for the in-lab visit within four weeks of the enrollment visit. A study physician will advise participants as to whether they should take their prescription medication during the fasting period prior to Visit 2. Note that the office visit (enrollment) and the laboratory visit (testing) may be combined, if logistically feasible.

9.1.3. Visit 2: Laboratory visit for testing

Participants will be asked to attend Visit 2 for daytime testing in the fasting state (no food or drink for four hours). The visit is anticipated to take approximately three hours. Prior to any testing, each participant will be guided through what to expect during the visit. Each participant will be given an opportunity to practice the breathing conditions described below prior to instrumentation.

Insertion of esophageal catheter

The gold-standard measurement of esophageal pressure will be made via a catheter surrounded by a small, sealed balloon placed in the lower esophagus, connected to a pressure transducer (Model 0585; Braebon Medical Corporation; Ontario, Canada). The site PI or their designee will administer local anesthetic in the form of lidocaine topical gel and/or spray to the nose and throat prior to insertion of the esophageal pressure balloon. The esophageal catheter will then be inserted through the nares, and placed in the lower esophagus for the duration of the testing procedures (approximately one hour). Calibration will be undertaken prior to testing.

Although generally well-tolerated, initiation and continuation of esophageal pressure measurement will depend on participant tolerance of instrumentation.

Placement of DreamKit device

The DreamKit device will be configured and placed on each participant per the supplied instructions.

Monitoring of other signals

Vital signs including, at minimum, finger pulse oximetry via the Alice 6 platform will be monitored throughout the data collection period.

Synchronization

Continuous viewing and recording of data from the esophageal catheter will take place via the Alice 6 and Sleepware, which is the system currently in use at the site. The site coordinator will ensure that these signals are free from artefact at initiation, and throughout the data collection period.

Document ID:	SRC_SLE_Sparkle EP 2_2021_11315	Document title:		Classification:	Confidential
Modified:	12 May 2021	Clinical Investigation Protocol ICH E6 Aligned			
Version:	1	User Tool ID:	16.2.6UserTool0004		
Status:	FINAL	User Tool Version Date	5June2019	Page:	20

Data from the DreamKit device will not be visible in real-time, and therefore it is important to ensure that the DreamKit signals can be synchronized to the esophageal pressure signals post-hoc. At the beginning and end of the data collection period, the participant will be asked to breathe out and hold their breath for approximately three seconds; then take a deep breath in and hold for approximately three seconds; and then finally, tap the DreamKit device to coincide with the peak of inhalation. This process will place a motion artefact on the accelerometry signal timed (approximately) to inhalation observed in the respiratory effort and esophageal pressure signals. The SpO₂ signals collected via the Alice 6 and the DreamKit device may also be used for time-alignment. During data processing, it may be necessary to make a small adjustment to the DreamKit time to match the Alice 6 time, ensuring synchronization of the signals.

Data Collection

Participants will be instructed to undertake the following breathing conditions (all in the supine position):

- End-expiratory breath holds to mimic central apneas: ten breath holds after exhalation, 10-20 seconds in duration.
- Occluded inspiration to mimic obstructive apneas: five periods of occluded inspiration paced at 15 attempted breaths/minute with blocked nose and mouth closed, 10-20 seconds in duration.
- Increased inspiratory resistance to mimic obstructive hypopneas and RERAs: paced at 15 breaths/minute against inspiratory resistance using the Philips IMT device (see details below), for 30 seconds at a time, five times.
- Increased expiratory resistance to mimic obstructive hypopneas and RERAs: paced at 15 breaths/minute against expiratory resistance using the Philips Threshold PEP device (see details below), for 30 seconds at a time, five times.
- Shallow breathing to mimic central hypopneas: partial breaths paced at 15 breaths/minute without resistance, for 30 seconds in duration, five times.
- Slow: paced at 12 breaths/minute; two minutes.
- Fast: paced at 20 breaths/minute; two minutes.
- Relaxed: paced at 15 breaths/minute; two minutes.

The coordinator will allow the participant time to become comfortable and still before beginning each condition, and will note the exact start/end time of each (MM:SS) from the computer used for data collection.

The participant may return to relaxed breathing at any time if they experience discomfort or dizziness.

For the paced breathing conditions, the site coordinator will play a metronome (e.g. www.imusic-school.com/en/tools-online-metronome) set to 24 (slow), 30 (relaxed) and 40 tones per minute (fast), allowing the participant to time each inspiration and expiration to the tones for breathing rates of 12, 15, and 20 breaths per minute.

Document ID:	SRC_SLE_Sparkle EP 2_2021_11315	Document title:		Classification:	Confidential
Modified:	12 May 2021	Clinical Investigation Protocol ICH E6 Aligned			
Version:	1	User Tool ID:	16.2.6UserTool0004		
Status:	FINAL	User Tool Version Date	5June2019	Page:	21

Increased inspiratory resistance will be achieved with the Philips Threshold IMT breathing trainer, a small, hand-held mouthpiece containing a flow-independent one-way valve¹. Similarly, increased expiratory resistance will be achieved with the Philips Threshold PEP device, a device which creates positive pressure during exhalation². The pressure of each device can be adjusted in 2cmH₂O increments. During data collection, the coordinator should coach the participant and adjust the pressure of each device when necessary in order to achieve appropriate changes in pressure during increased inspiratory and expiratory resistance conditions. Participants should aim to achieve a change from normal breathing of at least -15mmHg, but ideally -20 to -30mmHg, during the increased inspiratory and expiratory resistance conditions, and ensure a minimal change in esophageal pressure during the end-expiratory breath holds compared to normal breathing. A previous study following similar methodology to simulate apneas found a median change in esophageal pressure compared to normal breathing of -20.1mmHg (quartiles -21.9 to -15.0) with increased inspiratory resistance, -29.1mmHg (quartiles -38.4 to -20.6) with increased expiratory resistance, and 0.1mmHg (quartiles -2.9 to 2.0) with end-expiratory central apnea.^{10,11}

The data collection period is likely to be approximately one hour per participant, and will not exceed 1.5 hours. At this time, all equipment will be removed and the participant will be free to leave the laboratory.

Data processing

Using the timing information noted during data collection, an analyst blinded to the DreamKit data will score the esophageal pressure data files in order to identify the periods of occluded inspiration, end-expiratory breath-holds, increased inspiratory resistance, increased expiratory resistance, shallow breathing, slow respiration, fast respiration, and relaxed breathing. Periods of poor pressure signal quality will be excluded from analyses, such as artifact caused by movement, swallowing, or sensor displacement. An independent analyst will then import the DreamKit signal and ensure that the two data sources (Alice 6 and DreamKit) are synchronized following the procedures above. Periods where the DreamKit device indicates poor effort data quality by means of channel fail events will be excluded from analyses.

Follow-up phone call

A follow-up phone call will be placed 1-2 days after completion Visit 2, in order to assess any AEs that may have become apparent in the intervening period.

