4.2. Exploratory Objectives

Our exploratory objectives are:

- To repeat the analysis for the primary objective for each participant individually.
- Within the periods of occluded inspiration (representing obstructive apneas) and end-expiratory breath-holds (representing central apneas), to categorize each respiratory effort signal as being above or below a threshold of 10% of the baseline amplitude derived from normal (relaxed) breathing, in order to calculate sensitivity, specificity, and the area under the receiver operating characteristic (ROC) curve for the detection of obstructive events (overall and for each participant individually).
- Within the periods of increased inspiratory and expiratory resistance (representing obstructive hypopneas) and unresisted shallow breathing (representing central hypopneas), to calculate the area under the ROC curve in order to assess the agreement between the respiratory effort signals across all possible thresholds.

Document ID:	SRC_SLE_Sparkle EP 2_2021_11315	Document title:		Classification:	Confidential
Modified:	12 May 2021	Clinical Investigation Protocol ICH E6 Aligned			
Version:	1	User Tool ID:	16.2.6UserTool0004		
Status:	FINAL	User Tool Version Date	5June2019	Page:	13

- To compare the number of breaths/minute between esophageal manometry and the DreamKit device during relaxed breathing, fast breathing, slow breathing, occluded inspiration, increased inspiratory resistance, increased expiratory resistance, and unresisted shallow breathing.
- To evaluate the phase relationship between esophageal manometry and the DreamKit device during relaxed breathing, fast breathing, slow breathing, occluded inspiration, increased inspiratory resistance, increased expiratory resistance, and unresisted shallow breathing.

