12.2.5. Exploratory Analyses

The methodology described above for the primary analysis will be repeated using data from each participant individually.

Within the occluded inspiration and end-expiratory breath holds (representing obstructive and central apneas, respectively), we will categorize each signal as being above or below a threshold. Each period will be identified as a true positive for obstructive apnea (esophageal manometry scored as occluded inspiration and DreamKit signal above the threshold), true negative (esophageal manometry scored as breath-hold and DreamKit signal below the threshold), false positive (esophageal manometry signal scored as breath hold but DreamKit signal above the threshold), or false negative (esophageal manometry signal scored as occluded inspiration but DreamKit signal below the threshold). This will allow us to calculate the sensitivity, specificity, and area under the ROC curve for the ability of the DreamKit signal to identify obstructive apnea events. The threshold for calculating sensitivity and specificity will be 10% of the baseline amplitude derived from normal (relaxed) breathing. This threshold corresponds to a proportional change in respiratory effort for an apneic event that requires a 90% reduction of flow amplitudes as compared to the baseline respiration.

Document ID:	SRC_SLE_Sparkle EP 2_2021_11315	Document title:		Classification:	Confidential
Modified:	12 May 2021	Clinical Investigation Protocol ICH E6 Aligned			
Version:	1	User Tool ID:	16.2.6UserTool0004		
Status:	FINAL	User Tool Version Date	5June2019	Page:	28

Within the increased inspiratory/expiratory resistance and shallow breathing periods (representing obstructive and central hypopneas), we will calculate the area under the ROC curve which will provide an aggregate assessment of agreement between the two respiratory effort signals across all possible thresholds. Unlike apneas, the classification of hypopneas as obstructive or central is not based on the presence or absence of respiratory effort (AASM scoring criteria; Version 2.6), and therefore we will not categorize each breathing period on the basis of a respiratory effort threshold.

The respiratory rate will be extracted from each breathing condition except breath holds, and we will provide a Bland-Altman analysis of respiratory rate between the esophageal pressure signal and the DreamKit device.

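### The breathing-rate analysis pools conditions mostly paced at 15/min; agreement should be reported by paced rate, with a device-on-reference slope

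*Combined protocol and SAP*

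**What the plan says.** Breathing rate is an exploratory objective. Section 4.2 states it as: "To compare the number of breaths/minute between esophageal manometry and the DreamKit device during relaxed breathing, fast breathing, slow breathing, occluded inspiration", and goes on to list both resistance conditions and shallow breathing, seven conditions in all. Section 5.2.1 says the maneuvers were "designed to manipulate the rate, amplitude, and phase of the signals" to the greatest extent possible.

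Section 9.1.3 sets the pace of each condition:

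- Occluded inspiration: "five periods of occluded inspiration paced at 15 attempted breaths/minute with blocked nose and mouth closed, 10-20 seconds in duration".
- Inspiratory resistance: "paced at 15 breaths/minute against inspiratory resistance using the Philips IMT device (see details below), for 30 seconds at a time, five times".
- Expiratory resistance: "paced at 15 breaths/minute against expiratory resistance using the Philips Threshold PEP device (see details below), for 30 seconds at a time, five times".
- Unresisted shallow breathing: "partial breaths paced at 15 breaths/minute without resistance, for 30 seconds in duration, five times".
- Relaxed breathing: "Relaxed: paced at 15 breaths/minute; two minutes".
- Slow and fast breathing: one two-minute period each, at 12/min and 20/min.

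For the analysis, Section 12.2.5 says "The respiratory rate will be extracted from each breathing condition except breath holds", followed by a Bland-Altman comparison of the two devices. It does not say whether the unit is the period or the condition, whether results are split by paced rate, whether a slope or proportional bias will be examined, how repeated values are handled, or what agreement would be acceptable.

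**The concern.** Bland-Altman bias and limits are averages over the mix of true rates in the data. If nearly all values come from one imposed rate, the summary describes agreement at that rate and says little about whether the device follows a change in rate. An error that appears only at 12/min or 20/min is averaged with many values that cannot show it. The pooled limits could then be narrow although the device follows rate poorly, and they could be quoted as evidence that it follows rate well. This would still happen if repeated values within a participant were modelled correctly, because the cause is the concentration of reference rates.

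**Working it through.** The plan gives no precision, power or acceptance figure for rate, so there is none to reproduce. The inputs are the counts, durations and metronome settings in Section 9.1.3 and the ten evaluable participants in Section 12.1.

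**1. Paces.** The metronome is set to 24, 30 and 40 tones/min, with two tones per breath: 24/2 = 12, 30/2 = 15, 40/2 = 20. This agrees with the stated rates.

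**2. Share of the data at 15/min, breath holds excluded.**

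- By period: 5 + 5 + 5 + 5 + 1 = 21 at 15/min, plus one slow and one fast, gives 21/23 = 91%.
- By condition: 5/7 = 71%.
- By time: occlusions take 5 × 10–20 s = 0.83–1.67 min, the other three maneuvers 3 × 2.5 = 7.5 min, and relaxed breathing 2 min. That is 10.3–11.2 min at 15/min out of 14.3–15.2 min, or 72–74%.

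An error confined to slow and fast therefore enters the pooled mean with weight 2/23 = 9% by period, 2/7 = 29% by condition, or 26–28% by time.

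**3. Illustration: an output with no rate information.** Assume a device that always reports 15, participants who follow the metronome exactly, and ten participants. The difference (device minus esophageal) is 0 at 15/min, 15 - 12 = +3 at slow and 15 - 20 = -5 at fast. Over ten participants the sum of differences is 10 × (3 - 5) = -20 and the sum of squares is 10 × (9 + 25) = 340, whatever the number of zeros. With N values, bias = -20/N, SD = √[(340 - 400/N)/(N - 1)], and limits = bias ± 1.96 SD.

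| Unit | N | Bias | SD | Limits (breaths/min) |
|---|---|---|---|---|
| Period | 230 | -0.09 | 1.22 | -2.5 to +2.3 |
| Condition | 70 | -0.29 | 2.20 | -4.6 to +4.0 |
| Slow, relaxed, fast only | 30 | -0.67 | 3.36 | -7.2 to +5.9 |

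The device's errors are the same in every row; only the number of zeros changes. In the last row the slope of device rate on esophageal rate is 0, where a tracking device gives 1.

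**4. Imperfect metronome following.** With an assumed SD of 0.5 or 1.0 breaths/min around the target, the by-period limits become about -2.7 to +2.5 or -3.2 to +3.0. The by-condition limits become about -4.7 to +4.1 or -5.0 to +4.5. The pattern is unchanged.

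**5. Whether the existing data can show tracking.** For rates 12, 15 and 20 (mean 15.67), the sum of squared deviations is 13.44 + 0.44 + 18.78 = 32.67 per participant, or 326.7 for ten. With device error SD e, the slope's standard error is e/√326.7 = e/18.07. For an assumed e of 1 to 3 breaths/min and independent errors, this is 0.06 to 0.17, so slopes of 0 and 1 are easily separated. Using all 23 periods gives almost the same standard error (0.05 to 0.16), so the other twenty periods add almost nothing on tracking.

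**6. Why the maneuver periods belong apart.** At 15/min a 10–20 s occlusion holds 2.5–5 attempted breaths. Miscounting one breath moves the rate by 60/20 = 3 to 60/10 = 6 breaths/min in an occlusion, by 60/30 = 2 in a 30-second period, and by 60/120 = 0.5 in a two-minute period. These values differ in precision as well as in purpose.

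**The case against.** A reader might infer that the design cannot show rate tracking at all, or that any analysis of these data would be uninformative. The documents do not support that: every participant breathes at 12, 15 and 20/min for two minutes each, and step 5 shows this is enough to separate a tracking device from a non-tracking one.

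Agreement at 15/min is also not empty. The metronome sets the participant's rate, but the DreamKit rate has to be extracted from its own signal, so agreement during occlusion, resistance and shallow breathing tests whether breaths are detected when effort changes. That stands, and it is why those periods should be kept and reported.

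Nor would a constant output necessarily look good. The extraction wording in 12.2.5 refers to conditions, and by condition the limits span 4.6 + 4.0 = 8.6 breaths/min, more than the whole paced range of 20 - 12 = 8. For a constant output, difference = 30 - 2 × mean, a straight diagonal that a Bland-Altman plot would reveal. No acceptable limit is stated, so there is no benchmark for good. Nothing in the documents suggests DreamKit would default to 15; the constant output is only an extreme that shows the effect of pooling. Even so, 12.2.5 does not commit to the by-condition unit or to examining a slope.

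Finally, the wording in 5.2.1 covers rate, amplitude and phase together and contrasts the maneuvers with sleep recordings. A common pace in the maneuver conditions is defensible, since it avoids mixing rate with load. Section 9.1.3 varies rate less than 5.2.1 suggests but does not contradict it. Amplitude is primary (5.2.3), and the intended-use text in 4.3 makes no respiratory-rate claim.

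**Conclusion.** The point holds as a weakness of analysis. With 91% of periods, 71% of conditions or about 73% of recorded time at one paced rate, pooled bias and limits mainly describe agreement at 15/min and dilute any rate-dependent error. The size of the effect depends on the unit, which the plan leaves open: in the illustration the limits run from about ±2.4 breaths/min around near-zero bias by period to about -7.2 to +5.9 on the three conditions that vary rate. Those figures rest on a hypothetical constant output and exact pacing; modest departures from the metronome change them little. The objective is exploratory and the primary ICC is untouched, so this is a cheap improvement.

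**What to change.** In Section 12.2.5:

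- Report bias and limits of agreement separately at 12, 15 and 20/min, from the slow, relaxed and fast conditions, with the number of participants contributing at each rate.
- Report the within-participant slope of DreamKit rate on esophageal rate across these three conditions, with its confidence interval and a target of 1.
- Report the 15/min occluded, resisted and shallow periods separately, as a check of breath counting under altered effort, stating the unit and allowing for repeated values within participant.

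No new data or participant time is needed. The costs are somewhat more analysis, limits that may be wider and less favourable (each rests on at most ten values), and a minor amendment: Section 12 makes the SAP part of the protocol, and Section 1 requires IRB approval of protocol amendments. Spreading the maneuver repeats over other metronome rates is not recommended, because those maneuvers feed the primary ICC.
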